It is anticipated that approximately 1/3 of the 9,000 patients will have a large LRP, leading to complete follow-up in 3,000 patients with a large LRP and 3,000 with a small or no LRP.

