In multivariate analysis, we will assess the incremental prognostic value of lipid-rich plaques by fitting proportional hazards regression models that include the max 4mm LCBI value and other identified prognostic variables. To identify the variables to be included in the multivariate model, we will perform a step-up regression blinded to the NIRS and IVUS data to identify the prognostic factors other than NIRS or IVUS data associated with the NC-MACE outcome. When that model has been selected, max 4mm LCBI will be added to the model to assess its incremental prognostic value. This will be the definitive test of Hypothesis 1. Results from these analyses will be used to estimate the net reclassification improvement, a measure of the incremental prognostic value of a new prognostic variable. Weighted estimation will also be required to calculate the NRI. Other covariates to be considered as possible prognostic factors in the NRI analysis include but are not limited to age (10 year units), hypertension, diabetes (any), current smoking (at the time of NIRS evaluation), prior history of coronary disease, history of cardiovascular disease, BMI, index catheterization presentation status (ACS, unstable angina, stable angina, and positive EST), total cholesterol level, use of statin therapy at discharge (as well as prior to index catheterization), requirement for at least 1 lesion treatment at the time of index catheterization), ADP antagonist at discharge, plasma lipid levels at baseline and during follow-up if available and history of renal insufficiency.

In a secondary statistical analysis, we will investigate whether the location of a large LRP within a blinded or non-blinded NIRS recording modifies its association with subsequent NC-MACE events.

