To test Hypothesis 2 (the Vulnerable Plaque Hypothesis), we will treat the individual coronary artery segments as separate units of observation, with appropriate adjustment for clustering of segments within patients. A study participant will typically provide results for up to 9 segments. To test this hypothesis, we will fit a proportional hazards regression model with max 4mm LCBI in the coronary artery segment as the measure of exposure and NC-MACE during 24 months caused by a new culprit lesion in that segment as the outcome. All models will include a categorical variable representing the type of coronary artery segment. To identify other characteristics of the coronary artery that should be included in this analysis, we will perform an initial analysis blinded to the value of max 4mm LCBI to determine whether segment type, segment length, or other characteristics of individual segments are risk factors for NC-MACE. Identified segment characteristics will be included in the model used to test the primary hypothesis. All analyses of coronary artery segments will use generalized estimating equations with robust variances to account for clustering of segments within patients.

As in the vulnerable patient analysis, we will investigate the predictive value of the binary variables defined by varying cut-points of max 4mm LCBI. The analyses using various cut-points will be used to calculate an ROC curve characterizing the prognostic value of presence of a lipid-rich plaque in a coronary artery segment. Weighted estimation will be required to estimate the ROC curve because of the exclusion from follow-up of 3,000 of the 9,000 enrolled patients with no segments with max 4mm LCBI \geq 250 in the follow-up cohort and analyses will account for clustering of segments within patients.

Results from the multivariate analyses will be used to estimate the net reclassification improvement obtained by considering max 4mm LCBI of individual segments as a risk factor. Weighted estimation will again be required to calculate the NRI. The covariates considered in the vulnerable patient analysis will again be considered in the vulnerable plaque analysis.

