6.2 SAMPLE SIZE CONSIDERATIONS

A total of 9,000 patients will be enrolled with multi-vessel scans. It is expected based on the PROSPECT Study that at least 720 patients (8%) will experience a NC-MACE event. We expect to find approximately 3,000 patients with large LRP (max 4mm LCBI \geq 250). All 3,000 of these patients will be followed with phone calls for 2 years to identify those who have an event. We expect to observe at least 300 events in this group. From the 6,000 with no or small LRP, a random sample of 3,000 patients will also be followed to determine their event rate, and to examine with IVUS and angiograms those in whom events occur. Of the approximately 2,700 patients with large LRP who do not have an event, a 300 person sample will be selected for IVUS and angiographic analysis to investigate characteristics of the yellow spots that did not lead to events.

Vulnerable Patient Analysis

For hypothesis 1, we will test the hypothesis that there will be no association between the baseline value of max 4mm LCBI (over the entire area scanned) and the incidence of NC-MACE.

In PROSPECT registry results, the 24-month cumulative incidence of NC-MACE in patients was approximately 10%. Subsequent STEMI literature indicates that patients with large LRP will have a higher rate than that observed in PROSPECT.

For the power calculations below, we assumed 6,000 evaluable patients, an event rate between 4 and 8% in the overall LRP study, and a two-sided alpha of 0.05 with a standard deviation of 100 for max 4mm LCBI. Table 2

provides values for the power of the study to detect the following effect sizes: hazard ratio of 1.18, 1.20, and 1.22 per 100 unit increase in max 4mm LCBI (calculated in PASS 12). These results demonstrate that the study will have 80% power to detect a minimal effect size of 1.18 per 100 unit increase in the max 4mm LCBI with 6,000 patients and an overall cumulative incidence of 5% at 24 months. As described in section 5.3, interim analyses will be performed at 6 month intervals.

Table 2: Hypothesis 1: Power Calculation for Vulnerable Patient Hypothesis

2 Year cumulative incidence overall, patient level	Relative Risk per 100 unit increase in max 4mm LCBI		
	1.18	1.20	1.22
8%	0.95	0.98	0.99
7%	0.92	0.96	0.98
6%	0.88	0.93	0.97
5%	0.82	0.88	0.93
4%	0.73	0.81	0.87

Vulnerable Plaque Analysis

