For hypothesis 2, we will test the hypothesis that there will be no association between the baseline value of max 4mm LCBI of the proximal, mid, or distal segment of a coronary artery and the incidence of NC-MACE.

For the vulnerable plaque analysis, we assumed that a patient will have a minimum of 50 mm of scanned target artery within at least 2 native epicardial arteries, yielding a minimum of 4 segments. Assuming that 24,000 segments (from 6,000 patients) will be available for analysis, a two sided alpha of 0.05 and a standard deviation of 100 LCBI units for max 4mm LCBI, Table 3 provides values for the power of the study to detect the following effect sizes: hazard ratio of 1.18, 1.20, and 1.22 (calculated by PASS 12). The study will have 80% power to detect a minimum effect size of 1.18 per 100 unit increase in the max 4mm LCBI with the minimum expected number of segments (24,000) and an overall cumulative incidence of 1.25% within the segments at 24 months.

Table 3: Hypothesis 2: Power Calculation for Vulnerable Plaque Hypothesis

2 Year cumulative incidence overall, segment level	Relative Risk per 100 unit increase in max 4mm LCBI		
	1.18	1.20	1.24
1.75%	0.92	0.96	0.98
1.50%	0.88	0.93	0.97
1.25%	0.82	0.88	0.93
1.00%	0.73	0.81	0.87
0.75%	0.60	0.69	0.76

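### Tables 2 and 3 give power for an unadjusted test on independent units with no loss, so they do not demonstrate 80% power at HR 1.18 for the adjusted and clustered tests that decide the study

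*Combined protocol and SAP*

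**What the plan says.** For the patient-level power calculation, Section 6.2 states that "we assumed 6,000 evaluable patients, an event rate between 4 and 8% in the overall LRP study, and a two-sided alpha of 0.05", and takes the SD of the LCBI measure to be 100 units. It concludes: "These results demonstrate that the study will have 80% power to detect a minimal effect size of 1.18 per 100 unit increase", with 6,000 patients and 5% incidence at 24 months; the Table 2 cell is 0.82. For the segment level it writes "Assuming that 24,000 segments (from 6,000 patients) will be available for analysis", keeps the same alpha and SD, and claims 80% power at 1.18 with 1.25% incidence per segment; the Table 3 cell is again 0.82. The section gives no correlation between LCBI and other covariates, no loss to follow-up and no design effect.

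The 6,000 evaluable patients are the whole followed cohort. Section 4.2 describes the enrolment as "leading to complete follow-up in 3,000 patients with a large LRP and 3,000 with a small or no LRP".

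Section 6.1 begins Hypothesis 1 with a univariate Cox model. It then adds LCBI to a selected covariate model and says of that analysis: "This will be the definitive test of Hypothesis 1". For Hypothesis 2 it says "All models will include a categorical variable representing the type of coronary artery segment", adds other segment characteristics found to be prognostic, and uses generalized estimating equations with robust variances. Section 6.3 bases the interim decision on the multivariate analyses and tests at the end at the same Pocock level as at the interim looks.

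**The concern.** The power statement and the deciding tests do not match. Adjusting for covariates that are correlated with LCBI reduces the information on its coefficient. Loss to follow-up reduces the number of events. Positive within-patient correlation of both exposure and outcome can inflate the variance in the segment analysis.

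Some such correlation is plausible on the protocol's own content. The candidate covariates for Hypothesis 1 include diabetes, cholesterol, plasma lipids, statin use and presentation status. Section 2.1 says that vulnerable plaques lie mostly in proximal and mid segments (and distally in the right coronary artery), which suggests that segment type may be related to segment LCBI.

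What is at stake is the minimum detectable effect quoted for the design, and the remark in Section 6.3 that power is excellent, which relies on these tables.

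**Working it through.** **Inputs from Section 6.2.** N = 6,000 patients or 24,000 segments; SD = 100 LCBI units, so that 100 units is one SD; two-sided alpha 0.05 (z = 1.960); HR 1.18, 1.20 and 1.22. Events D = N × incidence.

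**Formula.** Cox model with a continuous exposure:

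power = Φ( √[D × (1 − R²) × (1 − loss) / DEFF] × ln(HR) − 1.960 )

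R² is the squared multiple correlation of LCBI with the other covariates. DEFF is the design effect, which applies to Hypothesis 2 only.

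**Step 1: reproduce the plan (R² = 0, loss = 0, DEFF = 1).**
- Table 2, 5%: D = 6,000 × 0.05 = 300; √300 × ln 1.18 = 17.321 × 0.16551 = 2.867; Φ(2.867 − 1.960) = 0.818 (plan 0.82).
- Table 2, 4%: D = 240 gives 0.727 (plan 0.73). At 8%: D = 480 gives 0.952 (plan 0.95).
- Table 3, 1.25%: D = 24,000 × 0.0125 = 300, again 0.818 (plan 0.82).
- All 15 cells of each table agree within 0.01. The third column of Table 3 reproduces at HR 1.22, as in the text, and not at its heading of 1.24 (which would give 0.961 rather than 0.93 at 1.25%).

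The tables agree wherever their event counts agree, so Table 3 contains no design effect.

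**Step 2: the reserve.** Events needed for 80% power at 1.18: (1.960 + 0.842)² / (ln 1.18)² = 287 (286.5 unrounded). Reserve at 300 events: 1 − 286.5/300 = 4.5%.

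The followed cohort is half large-LRP patients, against one third of those enrolled, so a 5% incidence in the whole study implies slightly more than 300 events among those followed. With normally distributed LCBI and HR 1.18 per SD (both assumptions) the number is about 314, and the reserve is 1 − 286.5/314 = 8.8%.

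**Step 3: Hypothesis 1 under assumed R² and loss (HR 1.18, alpha 0.05).**

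| R² | Loss | Retained | Power, 5% (300 events) | Power, 8% (480 events) | HR with 80% power at 5% |
|---|---|---|---|---|---|
| 0 | 0 | 1.00 | 0.82 | 0.95 | 1.18 |
| 0.10 | 0 | 0.90 | 0.78 | 0.93 | 1.19 |
| 0.10 | 5% | 0.855 | 0.76 | 0.92 | 1.19 |
| 0.10 | 10% | 0.81 | 0.73 | 0.90 | 1.20 |
| 0.20 | 10% | 0.72 | 0.68 | 0.87 | 1.21 |

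The incidence at which 80% at 1.18 holds is 286.5/(6,000 × retained): 5.6% for the third row and 6.6% for the last.

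**Step 4: Hypothesis 2 under an assumed design effect (300 events).** DEFF = 1 + (m − 1) × ρx × ρy, with m = 4 segments (Section 6.2), assumed within-patient LCBI correlation ρx = 0.4, and ρy = p(RR − 1)/(1 − p), where p = 1.25% and a second event is assumed 5 to 10 times as likely after a first.
- RR 5: ρy = 0.0125 × 4/0.9875 = 0.051; DEFF = 1 + 3 × 0.4 × 0.051 = 1.06; power 0.795.
- RR 10: ρy = 0.0125 × 9/0.9875 = 0.114; DEFF = 1.14; power 0.77.
- With an assumed segment-type R² of 0.05 in addition: 0.77 and about 0.74 to 0.75.

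**The case against.** The strongest reply is that the tables are arithmetically right and the 80% sentence is conditional on a pessimistic incidence. Section 6.2 expects at least 720 events in 9,000 patients (8%). At 480 events about 40% of the information can be lost before power at 1.18 falls below 80% (1 − 286.5/480 = 0.40). The protocol's own split (300 events among the 3,000 with a large LRP, hence 420 in the other 6,000) implies 300 + 420/2 = 510 events among those followed. This stands, and any restatement should show it.

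Other parts of the reply also stand:
- R², loss and the correlations are not in the documents. A step-up model may keep few covariates, so R² may be small.
- Multiplying events by (1 − loss) is conservative. The analysis is time-to-event, and a patient lost midway contributes until censoring.
- Clustering is the weakest of the three reasons. LCBI varies within a patient and events are rare, and with smaller correlations the design effect is close to 1. Clustering does not affect Hypothesis 1 at all.

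A reader might infer that the study fails to deliver 80% power at 1.18. The documents do not support that: a combined loss of information under 4.5% leaves the sentence true even at 300 events, and at 8% incidence it holds with room to spare.

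The reply does not rescue the wording. The plan itself ties 80% at 1.18 to 5% and 1.25% and presents the tables as demonstrating it. At those incidences the reserve is a few percent, and the calculation is for a test that Section 6.1 does not treat as definitive.

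**Conclusion.** The mismatch is established: both tables are unadjusted, independent-unit, zero-loss figures, and the deciding tests are not. The 80% claims at 5% and 1.25% incidence are therefore not demonstrated for those tests. That is weaker than saying they are false.

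The size is modest and depends on assumptions. At 5% incidence and alpha 0.05, Hypothesis 1 power lies between 0.68 and 0.78 for R² of 0.10 to 0.20 and loss of 0 to 10%, and the HR detectable with 80% power moves from 1.18 to about 1.19 to 1.21. For Hypothesis 2 the design effect alone takes power to between 0.795 and 0.77.

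The significance level is a separate matter, but it belongs in the same recalculation. With five interim looks and a final one, assumed equally spaced, the Pocock level is 0.0142. The final test alone then has power 0.66 at 300 events and HR 1.18 before any adjustment; power over all looks would be somewhat higher.

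**What to change.** Recompute Tables 2 and 3 and both 80% sentences for the deciding analyses:
- Use effective events = expected events in the followed cohort × (1 − loss) × (1 − R²), divided by a design effect for Hypothesis 2 only.
- State the R², loss and design effect used and the reason for each, and use the significance level that applies at the final test.
- Give a short sensitivity range that includes the 8% row.
- Restate either the HR detectable with 80% power (about 1.19 to 1.21 at 5% incidence and alpha 0.05, under the assumptions above) or the incidence at which 80% at 1.18 holds.
- Reconcile the third column heading of Table 3 (1.24) with the text (1.22), which is the value its entries match.

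The cost is text and tables only. No extra patients, procedures or analyses are needed, and the stated power becomes slightly less favourable.

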6.3 INTERIM ANALYSIS PLAN

As is evident from the power calculations provided in Section 5.2, for both the patient and segment level analysis, the LRP Study will have excellent power to detect relatively small increases in risk due to the presence of LRP.

The PROSPECT Study, with 700 patients, detected a hazard ratio of 5 for the presence of plaque burden > 70%. If the hazard ratio for increased LCBI reaches or exceeds 5, the LRP Study will provide definitive evidence that max 4mm LCBI predicts NC-MACE well before 6,000 patients have completed two-year follow-up. To provide an

opportunity for an early decision if this should occur, the LRP Outcomes Study will employ an interim analysis plan as described below.

When criteria for demonstrating an association between max 4mm LCBI and risk of NC-MACE have been met, the LRP Study will transition to a treatment study. This treatment study will include a control arm in which more detailed questions regarding the prognostic value of LCBI in various subgroups can be addressed in great detail.

The transition to a treatment study will require submission of a new protocol to the IRBs of the participating centers.

The interim analysis plan for the LRP Outcomes Study will be based on the Pocock spending function for repeated significance testing. This spending function will provide a greater opportunity for early stopping if strong associations emerge than would the O'Brien-Fleming or Haybittle-Peto spending functions. Specifically, review of accumulated data by the Data and Safety Monitoring Committee (DSMB) will occur on December 1, 2014 and at 6 month intervals thereafter until December 1, 2016. The DSMB will review the accumulated data to determine whether, in the multivariate analyses described in Section 5.1, both the vulnerable patient and the vulnerable plaque null hypotheses are statistically significant at the level required by the adjustment for repeated testing provided by the Pocock procedure. If those conditions are met, the DSMB may recommend termination of the study. If the study continues to the planned completion of two-year follow-up of all patients enrolled in the follow-up study, the two null hypotheses will be tested at the same significance level as that employed in the interim analyses. Additional information regarding the interim analysis plan will be provided in the Statistical Analysis Plan (SAP).

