3 ENDPOINTS

3.1 PRIMARY BASELINE MEASUREMENTS AND ENDPOINTS

For the Test of the Vulnerable Patient Hypothesis

The primary baseline measurement will be the maximum LCBI in 4 mm (max 4mm LCBI) over all scanned portions of the coronary arteries. The portion of artery to be scanned will exclude sites in which PCI has been performed in the past or will be performed in the index procedure (also excluding 5 mm borders of any site that underwent PCI).

The primary endpoint for the test of the vulnerable patient hypothesis will be the incidence of NC-MACE within 24 months.

The primary hypothesis is that risk of NC-MACE will be positively associated with max 4 mm LCBI measured as a continuous variable. The exposure-response relationship will also be evaluated for max 4 mm LCBI expressed as a binary variable above and below varying thresholds. It is hypothesized that increasing levels of max 4mm LCBI will identify increasing levels of risk for the patient of experiencing NC-MACE within 24 months following the artery imaging.

For the Test of the Vulnerable Plaque Hypothesis

The primary baseline measurement will be the maximum 4 mm LCBI detected in each proximal, mid, or distal segment of coronary artery scanned. The portion of artery to be scanned will exclude sites in which PCI has been performed in the past or will be performed in the index procedure (including 5 mm borders of any site that underwent PCI).

The primary endpoint for the test of the vulnerable plaque hypothesis will be the incidence of NC-MACE within 24 months.

The exposure-response function will be calculated for varying levels of max 4mm LCBI for each coronary artery segment. It is hypothesized that increased levels of max 4 mm LCBI in a coronary artery segment will identify increased levels of risk for that segment of causing NC-MACE within 24 months following the artery imaging.

FOLLOW-UP

All patients with a large LRP (defined as at least one 4mm segment with a max LCBI \geq 250 as assessed by IVUS-NIRS imaging) will be followed for 24 months to determine the occurrence of NC-MACE. Patients without at least one large LRP will be randomly allocated in a 1:1 ratio to 24 month follow-up or no follow-up.

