5 STUDY DESIGN

This is a prospective, multicenter, international study that will enroll 9,000 patients presenting for a clinically indicated cardiac catheterization with IVUS-NIRS interrogation for a culprit or suspected-culprit lesion. Patients will be screened for enrollment into the study after they provide written informed consent and undergo IVUS-NIRS imaging of at least 2 coronary arteries, including the Index Culprit Artery. If PCI is performed during the index procedure, the artery length for study inclusion will exclude the segment undergoing PCI plus a border of 5mm on either side of the PCI treated segment. Patients in whom IVUS-NIRS imaging is performed in only one artery will be considered screen failures.

It is expected that IVUS-NIRS imaging of the Suspected Index Culprit Artery will be performed for routine clinical indications. For this reason both NIRS and IVUS data from the culprit artery will be available in an unblinded fashion to the clinical site.

[figure not shown]
IVUS imaging of Index Non-Culprit Arteries may be of immediate clinical value (detection of an unexpected stenotic area) while NIRS imaging of Index Non-Culprit Arteries will be performed for research purposes. Hence for the Index Non-Culprit Arteries, IVUS data will be available to the clinical site, but NIRS data will be blinded.

Follow-up will be conducted in 6,000 patients (as defined in figure 1) at 2,6,12 and 24 months to determine the occurrence of a NC-MACE and the relationship of a Follow up Culprit Lesion to the baseline characteristics of the coronary artery segment.

The expected 9,000 patients will be enrolled at up to 100 centers throughout the world. It is expected that enrollment for the LRP Study will start in January, 2014 and conclude in or around December, 2015. Therefore, follow-up for the last patient enrolled will conclude in December 2017.

If the goals of the study – identification of vulnerable patients and vulnerable plaque by IVUS-NIRS imaging – are achieved before the enrollment of 9,000 patients, the study will transition to a blinded, randomized study of the use of IVUS-NIRS imaging to guide treatment.

Figure 1: Proposed flow of patients in the Lipid-rich Plaque Study

*if available

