6 STATISTICAL CONSIDERATIONS

6.1 STATISTICAL ANALYSIS

The Lipid-rich Plaque Outcomes Study is a global, multicenter prospective cohort study of patients who have undergone IVUS-NIRS coronary imaging to determine the extent and size of non-flow-limiting LRP's in their

coronary arteries. The objective of the study is to determine whether the presence of one or more LRPs is predictive of subsequent coronary events. A patient-level (Vulnerable Patient) and a plaque-level analysis (Vulnerable Plaque) will be conducted.

Primary Hypotheses:

The study will test two primary hypotheses, stated here in terms of the null hypothesis:

H1: Vulnerable Patient Hypothesis – During 24-month follow-up after IVUS-NIRS imaging, there will be no association between the baseline value of max 4mm LCBI (over all coronary artery segments included in the analysis) and the incidence of non-culprit NC-MACE events. (This hypothesis will be tested with a time-to-event analysis as described below).

H2: Vulnerable Plaque Hypothesis – During 24-month follow-up, there will be no association between the max 4mm LCBI of the proximal, mid, or distal segment of a coronary artery and the incidence of a culprit lesion in that segment leading to a NC-MACE event.

Additional Objectives:

As noted above, the study will also investigate the prognostic value of multiple novel NIRS measures and conventional IVUS measures that can be evaluated in multiple ways.

Statistical Methods:

To test Hypothesis 1 (the Vulnerable Patient Hypothesis), we will first fit a univariate proportional hazards regression model in which max 4mm LCBI is the only independent variable and NC-MACE is the outcome. The null hypothesis will be tested by the Wald test that the regression coefficient in a proportional hazards regression model is significantly different from 0. This analysis will determine whether max 4mm LCBI is a risk factor for NC-MACE. In supportive analyses, we will assess the validity of the proportional hazards assumption. We will also investigate the predictive value of the binary variables defined by varying cut-points of max 4mm LCBI. The analyses using these cut-points will be used to calculate an ROC curve characterizing the prognostic value of presence of a lipid-rich plaque. Weighted estimation will be required to estimate the ROC curve because of the underrepresentation of 3,000 individuals (absence of follow-up data) with no segments with max 4mm LCBI \geq 250 in the follow-up cohort.

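### Section 6.3 allows the study to be terminated at looks where no patient has 24 months of follow-up, and does not secure the remaining follow-up of patients already enrolled

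*Combined protocol and SAP*

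**What the plan says.** Section 3.1 sets the horizon: "The primary endpoint for the test of the vulnerable patient hypothesis will be the incidence of NC-MACE within 24 months". Section 2.1.1 and both primary hypotheses in Section 6.1 use the same 24 months.

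Section 5 gives the calendar: "It is expected that enrollment for the LRP Study will start in January, 2014 and conclude in or around December, 2015", and "follow-up for the last patient enrolled will conclude in December 2017". Table 1 and Section 5.1.4 schedule contacts at 60 days and at 6, 12 and 24 months, with no protocol-driven catheterization.

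Section 6.3 says that DSMB review of the accumulated data "will occur on December 1, 2014 and at 6 month intervals thereafter until December 1, 2016". The stopping condition is that both primary null hypotheses are rejected, in the multivariate models, at the Pocock-adjusted level. Then: "If those conditions are met, the DSMB may recommend termination of the study". The following sentence covers the other branch, in which the study runs on until two-year follow-up is complete and is tested at the same level. Section 6.3 sets no minimum follow-up, event count or effect size, and leaves further interim detail to the SAP.

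Section 5 adds that if the study's goals "are achieved before the enrollment of 9,000 patients, the study will transition to a blinded, randomized study". On the model, Section 6.1 says: "In supportive analyses, we will assess the validity of the proportional hazards assumption".

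**The concern.** The objective is stated at 24 months, but the rule can be met before anyone has been observed that long. The wording concerns the study, not enrolment, and it presents completed follow-up as the alternative to termination. Read literally, a crossing could end the contacts of patients already enrolled, and their second-year data would then not be collected.

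Two things are at stake. First, whether max 4mm LCBI still predicts events in the second year could be judged only from whatever late follow-up existed at the stop. The proportional hazards check is supportive, is not a condition for stopping, and has little to work on in months that are barely observed. Second, an estimate taken at an early Pocock crossing tends to exceed the true hazard ratio, and that estimate would inform the treatment study. Section 6.3 motivates early looks by a hazard ratio of 5 or more, but the rule is significance alone, so much smaller effects can trigger it.

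**Working it through.** **Inputs.** Enrolment dates (Section 5), look dates (Section 6.3), and 6,000 followed patients, 4 to 8% incidence, SD 100, two-sided alpha 0.05 and a smallest hazard ratio of 1.18 per 100 units (Section 6.2). Assumptions not in the documents: uniform accrual from 1 January 2014 to 31 December 2015, and a constant hazard.

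**Plan's own figure.** Power = Φ(√D × ln HR − 1.96). With D = 6,000 × 0.05 = 300 and HR 1.18: 17.32 × 0.1655 − 1.96 = 0.907, so power is 0.818. Table 2 gives 0.82, so the planning model is reproduced.

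**Follow-up at each look.** Let t be months from first possible entry.
- Looks 1 to 3 (t below 24): longest follow-up is t, mean is t/2, and information fraction is (t/24) × (t/2)/24 = t²/1152.
- Looks 4 and 5: the share with 24 months is (t − 24)/24. Mean capped follow-up is 5 + (19/24) × 14.5 = 16.5 at t = 29, and 11 + (13/24) × 17.5 = 20.5 at t = 35. Dividing by 24 gives the information fraction.

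| Look | Longest (months) | Mean (months) | With 24 months | Information | Events of 300 |
|---|---|---|---|---|---|
| 1 Dec 2014 | 11 | 5.5 | 0% | 0.105 | 32 |
| 1 Jun 2015 | 17 | 8.5 | 0% | 0.25 | 75 |
| 1 Dec 2015 | 23 | 11.5 | 0% | 0.46 | 138 |
| 1 Jun 2016 | 29 | 16.5 | 21% | 0.69 | 206 |
| 1 Dec 2016 | 35 | 20.5 | 46% | 0.85 | 256 |

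If entry instead runs from 31 January 2014 to 1 December 2015, the longest follow-up at looks 1 to 3 is 10, 16 and 22 months, and the shares at looks 4 and 5 are 18% and 45%. The three zeros depend only on the start date, not on the accrual pattern.

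**Scheduled contacts.** The earliest 24-month contact is 1 January 2016 less the 30-day window, that is 2 December 2015, one day after look 3. The last scheduled contact that any patient can have reached is therefore the 6-month one at look 1 and the 12-month one at looks 2 and 3.

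If events were known only through completed contacts, observed time per unit of accrual would be:
- Look 1: 4×2 + 5×6 = 38
- Look 2: 4×2 + 6×6 + 5×12 = 104
- Look 3: 4×2 + 6×6 + 11×12 = 176

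Out of 24 × 24 = 576, and with 300 final events, that is about 20, 54 and 92 events, against 32, 75 and 138 by elapsed time.

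**Second-year information at look 3.** Total person-time is 23²/2 = 264.5. The part beyond month 12 is 11²/2 = 60.5, or 23%.

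**Estimate at a crossing.** For five interim looks plus the final analysis at these information fractions, the simulated Pocock constant is 2.475 (nominal level 0.013; 2.450 and 0.014 with equal spacing). The smallest hazard ratio that can cross is exp(2.475/√events):
- Look 1: exp(2.475/√32) = 1.55
- Look 2: exp(2.475/√75) = 1.33
- Look 3: exp(2.475/√138) = 1.23

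If the true value is 1.18, every crossing in the expected direction at looks 1 to 3 overstates it.

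**Chance of an early crossing.** The look statistics are taken as correlated normals with mean √(events) × ln HR. At HR 1.18, H1 alone crosses by looks 1, 2 and 3 with cumulative probability 0.06, 0.17 and 0.34 for 300 final events, and 0.10, 0.28 and 0.53 for 480 (8% incidence). A separate Cox simulation (400 runs, HR 1.18, 5% incidence) gave 30% crossing by look 3, with a mean estimate of 1.40 at crossing. These are upper limits on early stopping, because H2 must also cross.

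**The case against.** The strongest reply is that an early decision is the plan's stated purpose. The hypotheses are nulls of no association, and Section 6.3 makes the transition depend on showing an association, not on a 24-month risk estimate. Cox regression handles censoring. The DSMB only may recommend termination, both hypotheses must cross, and further detail is deferred to the SAP. Sections 2.1.1 and 3.1 promise 24 months of follow-up with no exception for an interim stop, and Section 5.2 accepts only withdrawal of consent. All of this stands. It makes the fate of enrolled patients ambiguous rather than settled, but it does not remove the ambiguity that Section 6.3 creates.

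A reader might infer more than the documents support:
- *That an early stop rests on at most 12 months of data.* Twelve months is the last scheduled contact at looks 1 to 3 and close to the highest mean. Elapsed follow-up reaches 17 and 23 months, and 11/23 = 48% of those enrolled at look 3 have at least 12 months. Section 5.1.4 also allows medical record review.
- *That every early stop lacks 24-month data.* Looks 4 and 5 have some.
- *That the early test is invalid.* It is not, if hazards are proportional.
- *That stopping by look 3 is likely.* Crossing rates above 70% need hazard ratios of 1.3 or 1.4, which the documents do not give.
- *That a transition before full enrolment can happen only at looks 1 to 3.* The enrolment dates are expectations; slower accrual would extend this to later looks.
- *That the second-year question could never be answered.* Section 6.3 foresees a control arm in the treatment study for further prognostic questions, although nothing says that it would follow the present cohort.

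**Conclusion.** The point holds as a gap in the stopping rule, not as a flaw in the test. At three of five looks no patient has 24 months of observation, and at the other two fewer than half do. The rule nevertheless permits termination of the study on significance alone, without securing the rest of the follow-up. The claim at risk is the 24-month one: size of effect, persistence into the second year, and the ROC curve and NRI if evaluated at 24 months.

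The zeros at looks 1 to 3 rest only on the January 2014 start. The means, the shares at looks 4 and 5, and the event counts rest on uniform accrual and a constant hazard. At the plan's own hazard ratio of 1.18 and 5% incidence, the chance that H1 crosses by look 3 is about 30 to 34%, and that is an upper limit on stopping. The exposure is moderate, but the remedy is cheap enough to be worth making before the first look.

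**What to change.** Keep the five looks, the Pocock boundary and the early decision. In Section 6.3, and to match in Section 5, state that:

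1. A boundary crossing at any look may end whatever enrolment remains and may trigger the transition to the treatment protocol. Wording that only ends enrolment would be empty at looks 4 and 5 if enrolment closes on schedule, so the transition needs to be named too.
2. Every patient already allocated to follow-up completes the remaining scheduled contacts through 24 months.
3. The 24-month hazard ratio, ROC curve and NRI are reported from that completed follow-up, with separate hazard ratios for months 0 to 12 and 12 to 24 as a supportive analysis.

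The cost is protocol wording, plus follow-up calls and site payments that continue for up to 24 months after an early stop. Those contacts are already planned. No new patients or procedures are needed, and the treatment protocol need not wait for them.
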